6.2.3.2 Serious

An adverse event or suspected adverse reaction is considered *serious* if, in the view of either the investigator or sponsor, it results in any of the following outcomes:

- Death
- Life-threatening adverse event
- Inpatient hospitalization or prolongation of existing hospitalization
- A persistent or significant incapacity or substantial disruption of the ability to conduct normal life function
- Congenital anomaly/birth defect

Important medical events that may not result in death, are life-threatening, or require hospitalization may be considered serious when, based upon appropriate medical judgment, they may jeopardize the participant and may require medical or surgical intervention to prevent one of the outcomes listed in this definition. Examples of such medical events include allergic bronchospasm requiring intensive treatment in an emergency room or at home, blood dyscrasias or convulsions that do not result in inpatient hospitalization, or the development of drug dependency or drug abuse.

6.2.3.3 Life-threatening

An adverse event or suspected adverse reaction is considered life-threatening if, in the view of either the investigator or sponsor, its occurrence places the participant at immediate risk

of death. It does not include an adverse event or suspected adverse reaction that, had it occurred in a more severe form, might have caused death.

6.2.4 Recording of Adverse Events

Refer to the Data Safety Monitoring Plan, located in Appendix 2.

6.2.5 Follow-up of Adverse Events

All participants who experience adverse events will be followed with appropriate medical management until resolved or stabilized, as determined by the investigator. For selected adverse events for which administration of the investigational product was stopped, a re-challenge of the subject with the investigational drug may be conducted if considered both safe and ethical by the investigator.

6.2.6 Adverse Events Monitoring

Refer to the Data Safety Monitoring Plan, located in Appendix 2.

6.2.7 Expedited Reporting

Reporting to the Data and Safety Monitoring Committee

If a death occurs during the treatment phase of the study or within 30 days after the last administration of the study drug(s) and it is determined to be related either to the study drug(s) or to a study procedure, the Investigator or his/her designee must notify the DSMC Chair (or qualified alternate) within 1 business day of knowledge of the event. The contact may be by phone or e-mail.

Reporting to Institutional Review Board

The UCSF PI must report events to the UCSF IRB according to institutional guidelines.

UCSF IRB website for guidance in reporting adverse events: <https://irb.ucsf.edu/adverse-event>

Expedited Reporting to the Food and Drug Administration (FDA)

If the study is being conducted under an IND, the Sponsor (or the Sponsor-Investigator) is responsible for determining whether or not the suspected adverse reaction meets the criteria for expedited reporting in accordance with federal regulations (21 CFR §312.32).

The Investigator must report in an IND safety report any suspected adverse reaction that is both serious and unexpected. The Sponsor needs to ensure that the event meets all three definitions:

- Suspected adverse reaction
- Unexpected
- Serious

If the adverse event does not meet all three of the definitions, it should not be submitted as an expedited IND safety report.

The timeline for submitting an IND safety report to FDA is no later than **15 calendar days** after the Investigator determines that the suspected adverse reaction qualifies for reporting (21 CFR 312.32(c)(1)).

Any unexpected fatal or life-threatening suspected adverse reaction will be reported to FDA no later than **7 calendar days** after the Investigator's initial receipt of the information (21 CFR 312.32(c)(2)).

Any relevant additional information that pertains to a previously submitted IND safety report will be submitted to FDA as a Follow-up IND Safety Report without delay, as soon as the information is available (21 CFR 312.32(d)(2)).

7 Statistical Considerations and Evaluation of Results

7.1 Imaging Analysis

A trained nuclear medicine physician will evaluate the reconstructed PET, CT or MRI, and fused PET/CT or PET/MR images using a PET volume computer-assisted reading software package. A positive lesion on PET will be defined as a focus of activity with higher SUV compared with mediastinal blood pool that is not attributable to other etiologies of tracer distribution (e.g. inflammation, excretion). A volume of interest (VOI) will be semi-automatically placed around each lesion, and the calculated maximum standard uptake value (SUV_{max}) will be recorded for each lesion, including lesions that are detected on standard scans but are not positive on PET. Adjusted SUV_{max} data will then be averaged the primary tumor and 5 largest lesions in each of three metastatic site (nodal, visceral, and osseous) within a given patient, up to a maximum of 16 lesions per patient ($SUV_{max-avg}$). Irradiated lesions will be excluded from this analysis.

7.2 Sample Size Considerations

7.2.1 Sample Size and Power Estimate

The sample size of 100 evaluable patients is based on the primary study endpoint. Based on the available standard of care and investigational therapies available in mCRPC, it is estimated that 40% of patients will experience a PSA50 response on the systemic treatment chosen by investigator. Based on prior data from retrospective studies evaluating PSMA PET as an indicator of clinical response, patients with clinical response have an approximate 50% reduction from baseline in $SUV_{max-ave}$ on serial PSMA PET. A sample size of 100 patients (estimated 40 PSA50 responders, 60 non-responders) provides 89% power to detect an effect size of 0.67 with respect to the percent change from baseline in $SUV_{max-ave}$ on PSMA PET in PSA50 responders vs. non-responders, using the Mann-Whitney test and bi-directional alpha = 0.05. This translates into an absolute mean difference in the percent change from baseline on PSMA PET between responders vs. non-responders of 20% (within group SD 30%).

7.2.2 Accrual Estimates

The estimated accrual period is 18-24 months.

7.3 Interim Analyses

An interim analysis for feasibility will be performed after 30 patients are enrolled. Baseline and on-treatment PSMA PET images will be qualitatively reviewed and preliminary data with respect to the mean percent change from baseline in $SUV_{max-ave}$ will be determined. If it is determined that insufficient change is detected, adjustment of on-treatment PSMA PET scan time point may be instituted along with specification of the type of systemic therapy allowed post –baseline PSMA PET.

7.4 Analyses Plans

7.4.1 Analysis Population

All data from all subjects dosed in the study will be included in all listings, plots, summary tables, and statistical analyses when appropriate. Missing values will not be substituted by estimated values, but treated as missing in the statistical evaluation.

7.4.2 Primary Analysis (or Analysis of Primary Endpoints)

The mean ($SUV_{max,ave}$), median, and range of SUV_{max} across the primary tumor and the 5 largest lesions in each of three metastatic sites (nodal, visceral and osseous; for a maximum of 16 lesions per patient) will be descriptively reported. The study cohort will be divided into subgroups based on whether or not patient experienced a $\geq 50\%$ decline from baseline in serum PSA (PSA50 responder) or not (PSA50 non-responder). The mean percent change from baseline in $SUV_{max,ave}$ on PSMA PET between PSA50 responders vs. non-responders will be compared using the Mann-Whitney test.

7.4.3 Secondary Analysis (or Analysis of Secondary Endpoints)

The study cohort will be dichotomized by the median with respect to percent change from baseline in $SUV_{max,ave}$ on PSMA PET. The time-to-event variables including PSA progression-free defined by PCWG3, and overall survival will be compared between dichotomized subgroups using the log-rank test. Kaplan-Meier product limit method will be used to estimate median survival in each subgroup.

Amongst the subset of measurable soft tissue lesions by RECIST 1.1 criteria, on a per-lesion basis, the mean percent change from baseline in SUV_{max} on PSMA PET will be compared between responding lesions by RECIST 1.1 criteria vs. those without response, using Mann-Whitney test.

PSMA negative lesions will be defined as those with SUV values below the mediastinal blood pool. Low positive lesions will be defined as those with SUV_{max} values above the blood pool, but below background liver uptake. Intermediate positive lesions are those defined by SUV_{max} values above background liver, but below parotid gland uptake. High positive lesions are those with SUV_{max} values above that of parotid gland. The histologic, genomic and transcriptional features of each subgroup of PSMA lesion category that has matching tumor tissue will be descriptively reported with particular emphasis on the low and negative PSMA lesions that have paired tumor tissue available.

The median and range for inter-tumoral SUV_{max} across metastatic lesions within individual patients will be descriptively reported, to assess for heterogeneity of PSMA uptake. The cohort will be dichotomized above and below median range of SUV_{max} values to define low and high heterogeneity subgroups. Overall survival from date of onset of mCRPC will be compared between high vs. low heterogeneity subgroups.

Analysis of the correlation between SUV_{max} PSMA and FDG PET will be performed on a per-lesion basis amongst the subset of patients who have paired evaluable imaging using Pearson r correlation coefficient.

Patterns of PSMA expression at the time of progression by PCWG3 criteria will be descriptively characterized.

Comparison of mean percent change from baseline in $SUV_{max,ave}$ in PSA50 responders vs. non-responders will be performed in pre-specified subgroups based on modality of systemic

treatment, including AR targeted therapy, PSMA-directed radioligand therapy, cytotoxic chemotherapy, and immunotherapy.

No adjustment will be made for multiple comparisons for the analysis of the secondary and exploratory endpoints.

8 Study Management

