2.3 Secondary Objective(s) and Endpoint(s)

Secondary Objective	Endpoint(s)	Time Frame
1. To determine whether the percent change from baseline in $SUV_{max-ave}$ on PSMA PET is associated with time-to-event endpoints including PSA progression-free survival by Prostate Cancer Clinical Trials Working Group 3 (PCWG3) ²⁶ criteria and overall survival.	Association between percent change from baseline in $SUV_{max-ave}$ on PSMA PET with time-to-event endpoints including PSA progression-free survival by PCWG3 criteria and overall survival.	Baseline to time of progression Baseline to time of death
2. To determine whether the percent change from baseline in SUV_{max} on PSMA PET is associated with objective response by Response Evaluation Criteria in Solid Tumors (RECIST) version 1.1 ²⁷ on a per-lesion basis among measurable soft tissue lesions present at baseline	Association between percent change from baseline in SUV_{max} on PSMA PET with objective response by RECIST 1.1 on a per-lesion basis among measurable soft tissue lesions present at baseline.	Baseline to time of objective response

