3.2 Sample Size

Approximately 110 patients will be consented to achieve the target number of 100 evaluable participants (this includes both sub-cohorts A1 & A2).

Participants who did not complete paired PSMA PET imaging, those with negative baseline PSMA PET, or those who did not subsequently start a new systemic therapy for treatment of mCRPC following baseline PSMA PET will be considered unevaluable for the primary analysis and will be replaced.

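### PSA-PFS and OS are related to SUV change only through a sample-median split, which is valid but usually less efficient than a continuous model and gives no effect per unit of change

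*Combined protocol and SAP*

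**What the plan says.** The first secondary objective (section 2.3) asks whether percent change from baseline in SUVmax-ave is associated with PSA-PFS and OS. Section 7.4.3 gives the analysis: "The study cohort will be dichotomized by the median with respect to percent change from baseline in" SUVmax-ave, after which PSA-PFS and "overall survival will be compared between dichotomized subgroups using the log-rank test". Kaplan-Meier medians are added for each half. The plan contains no Cox model, no hazard ratio with confidence interval, and no other analysis that keeps the percent change continuous.

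The heterogeneity analysis in section 7.4.3 has the same design: "The cohort will be dichotomized above and below median range of" SUVmax values, and OS is then compared between the two groups. No test is named there. Section 2.4 lists this objective as exploratory.

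The primary analysis (section 7.4.2) differs: it compares the ungrouped percent change between PSA50 responders and non-responders by Mann-Whitney test.

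On size, section 3.2 says "Approximately 110 patients will be consented to achieve the target number of 100 evaluable participants". Section 7.2.1 powers the primary comparison only. No event count, hazard ratio or power is given for PSA-PFS or OS.

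**The concern.** The objective concerns the percent change itself, but the analysis uses only which half of the sample a patient falls in. Section 7.2.1 puts responders at about a 50% reduction and the groups 20 points apart, which implies about a 30% reduction in non-responders. With a 40/60 mix and SD 30, the sample median would then lie near -38%. Patients at -37% and -39% would be treated as opposites, and patients at -39% and -90% as the same.

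Nothing in the plan says why the median should matter biologically. It will also move with case mix: therapy is at the physician's discretion (section 5.3.5), scan timing differs by treatment class (section 5.3.6), and the interim look may change both scan timing and permitted therapy (section 7.3).

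Two things are at stake. A real association is more likely to be missed if risk changes gradually with SUV change. And whatever is found will be a p-value and two medians, with no statement of how much risk changes for a given SUV change.

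**Working it through.** **1. The plan's own figure.** Section 7.2.1 has "estimated 40 PSA50 responders, 60 non-responders" and says the sample "provides 89% power to detect an effect size of 0.67", at two-sided 0.05. With the Mann-Whitney efficiency of 3/π = 0.955 relative to the t-test:

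sqrt(40 × 60 / 100 × 0.955) × 0.67 − 1.96 = 3.21 − 1.96 = 1.25, so power = Φ(1.25) = 89%.

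Simulated Mann-Whitney tests give 88-88.5%. The figure reproduces. It does not bear on the survival analyses, which have no power statement.

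**2. Information kept by a median split.** For a log-linear effect, this is the squared correlation between the marker and its above-median indicator.

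| Marker shape | Kept | Lost |
|---|---|---|
| Normal (2/π) | 64% | 36% |
| Mixture implied by section 7.2.1 (40/60, 20 points apart, SD 30) | 64% | 36% |
| Uniform (assumed) | 75% | 25% |
| t with 5 df (assumed) | 54% | 46% |
| Right-skewed: lognormal, exponential (assumed) | 47-52% | 48-53% |

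**3. Events needed for 80% power**, two-sided 0.05, normal marker. Continuous: (1.96 + 0.84)² / (ln HR per SD)². Split: the same multiplied by π/2 = 1.57.

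For HR 1.4 per SD: 7.85 / 0.1132 = 69.3, so 70 events. Split: 69.3 × 1.57 = 108.9, so 109 events. The corresponding HR between halves is exp(2 × 0.336 × 0.798) = 1.71.

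| HR per SD | Continuous | Split |
|---|---|---|
| 1.3 | 115 | 180 |
| 1.4 | 70 | 109 |
| 1.5 | 48 | 75 |

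**4. How many events?** The documents do not say, so this is an assumption. Take exponential survival, no loss to follow-up, uniform accrual over A = 24 months (the upper end of section 7.2.2) and a cut at T = 48 months (section 3.7). Then events = 100 × {1 − [exp(−λ(T−A)) − exp(−λT)] / (λA)}, with λ = ln 2 / median. Medians of 12, 24 and 36 months give about 86, 64 and 50 events. The ceiling is about 100 per endpoint.

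**5. Power at HR 1.4 per SD, normal marker, log-linear effect.** The first three rows are simulated (100 patients, Cox score test against log-rank on the split, 6,000 trials per row; repeat runs agree within about 2 points). The last row is by formula.

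| Events | Continuous | Split |
|---|---|---|
| 50 | 65% | 45-47% |
| 64 | 75% | 56% |
| 85 | 85% | 66% |
| 100 (ceiling) | 92% | 77% |

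**6. The opposite case.** Let the true effect be a step at the population median with HR 2, with about 64 events. The split then has about 71% power against 59% for a linear continuous term with a normal marker, and about 71% against 46% with a right-skewed marker. The ordering reverses.

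**The case against.** The strongest defence is that the planned test is sound. The cut is pre-specified and comes from the marker's distribution, not from the outcome. A reader might infer that a data-derived cut inflates the false-positive rate. It does not: the log-rank test keeps its type I error. The objective asks only whether an association exists, a two-group test answers that, and no effect per unit was promised. The endpoints are secondary and carry no power claim. All of this stands.

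Log-linearity is also open to doubt. Section 1.3 describes early rises in uptake despite PSA response, section 5.3.6 pools four treatment classes, and percent change is bounded at −100% but unbounded above, so a few large rises could dominate a linear term. This stands too. It limits the size of the claim and shapes the fix, but it does not justify having no continuous analysis.

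Three further readings go beyond the documents:

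- That the event count is small. The plan gives no number, and PSA-PFS events could approach the ceiling of about 100.
- That about a third of the information is lost in all circumstances. That figure needs a normal marker and a log-linear effect.
- That no other study could apply the cut. A reported median is a number others can use. The fair criticism is that it reflects this sample's mix and has no external rationale.

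Nor does the heterogeneity analysis share the secondary tier, although it is described in the secondary-analysis section.

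**Conclusion.** The point holds as a matter of efficiency and interpretability, not as an error. The median split is the only planned analysis of SUV change against PSA-PFS and OS. It is valid, but it rests on a sample-dependent cut without a rationale and gives no effect per unit of change.

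Under a normal marker with a log-linear effect, including the mixture implied by section 7.2.1, it loses about 36% of the information and needs about 1.57 times the events. The loss ranges over 25-53% for the other marker shapes tried, and there is none if the true effect is a step at the median. At HR 1.4 per SD, the power deficit is roughly 15 to 20 points from 50 events up to the 100-event ceiling. The event counts below that ceiling, the hazard ratio and the effect shape are assumptions, because the plan states none of them. The primary analysis and its 89% power are unaffected. The change should be made, but the trial's validity does not depend on it.

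**What to change.** In section 7.4.3, make the main secondary test for PSA-PFS and for OS a Cox model with change in SUVmax-ave as a continuous term, and report the hazard ratio per 10 or 30 points with a 95% CI (30 points is the within-group SD in section 7.2.1).

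Before outcomes are examined, also fix:

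- **The scale.** Choose a form that limits the influence of large rises, such as the log ratio of follow-up to baseline SUVmax-ave. If the log ratio is used, give the hazard ratio per halving and translate it into a contrast between two stated percent changes, so that the result still reads in percentage points.
- **The consequence of non-linearity.** Pre-specify a spline (knots and test) and state that the spline result is reported if non-linearity is found.

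Keep the median-split Kaplan-Meier curves and log-rank test as supportive display. Treat the heterogeneity-OS analysis the same way, name its test, and label it exploratory.

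The cost is analysis wording only: no new patients, scans or visits. The small downside is that the main test then depends on the chosen functional form, which the pre-specified scale, the spline and the retained split are there to contain.

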1.5 Overall Study Rationale

⁶⁸Ga-PSMA-PET has been shown to have significant utility and clinical impact in the detection of prostate cancer in newly diagnosed and biochemically recurrent patients. Preliminary retrospective evidence suggests that in patients with metastatic castration resistant prostate cancer, decline from baseline in PSMA PET upon application of systemic therapies in mCRPC may be associated with subsequent response, however this link has not been definitively established. A subset of patients with mCRPC may also present with low or heterogeneous PSMA expression, which may be associated with a poor prognosis. We aim to prospectively investigate the association between response on PSMA PET with subsequent treatment outcomes. We also hope to describe the clinical histologic, genomic features of patients with low or heterogeneous PSMA expression.

2 Study Objectives and Hypotheses

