3.1 Characteristics

This is a single site phase 2 prospective imaging study evaluating the utility of Ga-PSMA PET to detect treatment response in patients with metastatic castration resistant prostate cancer. There are two sub-cohorts:

- Sub-cohort A1: Patients with castration-resistant prostate cancer *planning* to start a new line of systemic therapy will be enrolled and undergo a baseline pre-treatment ⁶⁸Ga-PSMA-11 PET scan. Patients will then be monitored for treatment response and undergo a repeat ⁶⁸Ga-PSMA-11 PET scan 16 weeks (+/- 8 weeks) after the start of systemic therapy. (*Note: Patients in sub-cohort A1 who initiate systemic therapy during the screening period/prior to study enrollment may be re-consented to transition to sub-cohort A2.*)
- Sub-cohort A2: Patients with castration-resistant prostate cancer *currently* on systemic therapy will be enrolled if a baseline pre-treatment ⁶⁸Ga-PSMA-11 PET scan was performed within 12 weeks prior to the start of systemic therapy, and the on-treatment PSMA PET can be performed within 16 weeks (+/- 8 weeks) after the start of systemic therapy. Patients will then be monitored for treatment response and undergo a repeat ⁶⁸Ga-PSMA-11 PET scan 16 weeks (+/- 8 weeks) after the start of systemic therapy.

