5.1 Study Calendar

5.1.1 Study Calendar for Sub-Cohort A1

Period / Procedure	Screening (Within 12 weeks prior to C1D1)	Cycle 1 Day 1 (Start of systemic therapy) ¹⁰	Follow up Response Monitoring 8 weeks (+/- 4 weeks)	Follow up PET 16 weeks (+/- 8 weeks) Following Treatment Initiation ⁹	Disease Progression by PCWG3
Informed consent	X				
Baseline conditions	X				
Concomitant medications	X				
Demographics	X				
Serum PSA ¹	X		X	X	X
Performance status	X				
LDH, CBC + diff, Liver function tests	X				
Disease assessment by cross sectional imaging	X ²		X ³	X ⁴	X ⁴
⁶⁸ Ga-PSMA-11 PET/CT or PET/MRI	X ⁸			X	X (Optional)
Tumor biopsy ⁵ (optional)	X				
Circulating tumor nucleic acid collection ⁶ (optional)	X			X	X
FDG PET/CT ⁷ (optional)	X				

¹ Response monitoring with respect to serum PSA will occur per standard of care and provider discretion. A minimum of three serum PSA values are required including: at baseline prior to initiation of systemic treatment (+/- 12 weeks), at 8 weeks (+/- 4 weeks), and at 16 weeks (+/- 8 weeks).

² Cross-sectional imaging of the chest/abdomen/pelvis (CT or MRI; with IV contrast if medically permissible), including paired CT or MRI obtained with baseline PET scan.

³ Response monitoring with respect to conventional imaging will occur per standard of care and provider discretion.

⁴ Cross-sectional imaging of the chest/abdomen/pelvis (CT or MRI; with IV contrast if medically permissible), including paired CT or MRI obtained with PET scan. Patients who underwent PET/CT at baseline should have same imaging modality performed during follow-up, and likewise patients who underwent PET/MR at baseline should have same imaging modality performed for follow up PSMA PET imaging.

⁵ Metastatic tumor biopsy is optional for [eligible](#) participants. Tumor biopsy should be performed within 12 weeks following baseline PET. Soft tissue, PET-avid lesions should be prioritized for biopsy whenever feasible. Biopsy will be performed under companion protocol CC# 155518.

⁶ Circulating tumor nucleic acid collection via peripheral blood collection is optional. Collection will be performed under companion protocol CC # 155518.

⁷ FDG PET/CT is optional. FDG PET will be performed at baseline (+/ 12 weeks from date of baseline Ga-PSMA PET).

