5.1.2 Study Calendar for Sub-Cohort A2

Period / Procedure	Screening (Within 24 weeks after the start of current systemic therapy)	Follow up Response Monitoring 8 weeks (+/- 4 weeks)	Follow up PET 16 weeks (+/- 8 weeks) Following Treatment Initiation ⁷	Disease Progression by PCWG3
Informed consent	X			
Baseline conditions	X			
Concomitant medications	X			
Demographics	X			
Serum PSA ¹	X	X	X	X
Performance status	X			
LDH, CBC + diff, Liver function tests	X			
Disease assessment by cross sectional imaging	(X) ²	X ³	X ⁴	X ³
⁶⁸ Ga-PSMA-11 PET/CT or PET/MRI	(X) ^{5,6}		X	X (Optional)

¹ Response monitoring with respect to serum PSA will occur per standard of care and provider discretion. A minimum of two serum PSA values are required including: at baseline prior to initiation of systemic treatment (+/- 12 weeks), and at 16 weeks (+/- 8 weeks).

² Prior cross-sectional imaging of the chest/abdomen/pelvis (CT or MRI) performed within 12 weeks of the baseline ⁶⁸Ga-PSMA-11 PET scan (including paired CT or MRI obtained with baseline PET scan) may serve as a baseline and does not need to be repeated.

³ Response monitoring with respect to conventional imaging will occur per standard of care and provider discretion.

⁴ Cross-sectional imaging of the chest/abdomen/pelvis (CT or MRI; with IV contrast if medically permissible), including paired CT or MRI obtained with PET scan. Patients who underwent PET/CT at baseline should have same imaging modality performed during follow-up, and likewise patients who underwent PET/MR at baseline should have same imaging modality performed for follow up PSMA PET imaging.

⁵ A ⁶⁸Ga-PSMA-11 PET scan performed prior to study enrollment may serve as a baseline PSMA PET if performed within 12 weeks prior to the start of current systemic therapy. This scan is required within window as part of eligibility requirements (See [Section 3.3.1](#)). Patients must also have an on-treatment PSMA PET within 16 weeks (+/-8 weeks) after starting treatment.

⁶ At least one metastatic lesion with PSMA uptake at or above that of the blood pool will be required for study entry.

⁷ Specific timing of follow up PET to be determined based on modality of therapy (see [Section 5.3.6](#)).

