5.3.5 Initiation of Systemic Therapy

- Sub-cohort A1: Patients will subsequently initiate systemic treatment for castration resistant prostate cancer. Choice of therapy will be per discretion of the treating physician. Response monitoring with respect to serum PSA and conventional imaging will occur per standard of care and provider discretion. A minimum of three serum PSA values are required including at baseline within 12 weeks prior to initiation of systemic treatment, at 8 weeks (+/- 4 weeks), and at 16 weeks (+/- 8 weeks) from start of systemic therapy.
- Sub-cohort A2: Patients must be currently receiving systemic treatment for castration resistant prostate cancer, initiated within 12 weeks after their baseline 68Ga-PSMA -11 PET scan. Choice of therapy will be per discretion of the treating physician. Response monitoring with respect to serum PSA and conventional imaging will occur per standard of care and provider discretion. A minimum of two serum PSA values are required including at baseline within 12 weeks prior to initiation of systemic treatment and at 16 weeks (+/- 8 weeks) from start of systemic therapy.

5.3.6 Follow up ⁶⁸Ga-PSMA-11 PET (16 weeks +/- 8 weeks from date of systemic treatment initiation)

Patients will undergo repeat ⁶⁸Ga-PSMA-11 PET after 16 weeks (+/- 8 weeks) from date of initiation of systemic treatment.

The specific time frame for imaging will depend on the treatment modality administered, and will be standardized as follows:

- Androgen Receptor (AR) targeted therapy (20 weeks +/- 4 weeks)
- PSMA-targeting radioligand therapy (12 weeks +/- 4 weeks)
- Cytotoxic chemotherapy (12 weeks +/- 4 weeks)
- Immunotherapy (12 weeks +/- 4 weeks)

Patients with a negative baseline PSMA PET scan (i.e. no metastatic lesion with PSMA uptake at or above that of the blood pool) will not be eligible for the follow up PSMA PET.

Patients who underwent PET/CT at baseline should have same imaging modality performed during follow-up, and likewise patients who underwent PET/MR at baseline should have same imaging modality performed for follow up PSMA PET imaging.

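### The PSA-PFS comparison in 7.4.3 runs from baseline but groups patients by a week 8-24 PET, so a positive result cannot by itself show association with later progression

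*Combined protocol and SAP*

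**What the plan says.** - **Grouping and test (7.4.3).** Patients are split at the median percent change in SUVmax-ave, and "The time-to-event variables including PSA progression-free defined by PCWG3, and overall survival will be compared between dichotomized subgroups using the log-rank test". This paragraph names no time origin or landmark.
- **Clock (2.3).** The time frames for the two time-to-event endpoints are "Baseline to time of progression Baseline to time of death". Baseline is not tied to the PET date or to the start of therapy, which may be up to 12 weeks apart.
- **When the group is known (5.3.6).** "The specific time frame for imaging will depend on the treatment modality administered, and will be standardized as follows": weeks 16-24 for AR-targeted therapy and weeks 8-16 for the other three modalities. This is the only mandatory on-treatment PET.
- **PSA before the scan.** Sub-cohort A1: "A minimum of three serum PSA values are required including at baseline within 12 weeks prior to initiation of systemic treatment, at 8 weeks" (+/- 4) and at week 16 (+/- 8). Sub-cohort A2: "A minimum of two serum PSA values are required including: at baseline prior to initiation of systemic treatment" and at week 16 (+/- 8). Beyond these minimums, "Response monitoring with respect to serum PSA will occur per standard of care and provider discretion".
- **Purpose.** Section 1.5: "We aim to prospectively investigate the association between response on PSMA PET with subsequent treatment outcomes". Section 3.1: "This is a single site phase 2 prospective imaging study evaluating the utility of Ga-PSMA PET to detect treatment response".
- **What is not covered.** Section 3.2 makes patients without paired PET unevaluable for the primary analysis only. Section 7.4.1 says missing values are not imputed. Neither covers a patient who progresses by PSA and is then scanned. The second clock in 7.4.3, onset of mCRPC, belongs to a different analysis (OS by baseline heterogeneity).

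**The concern.** A patient's group is fixed 8-24 weeks after therapy starts, and up to 12 + 24 = 36 weeks after the baseline PET. The event clock is already running. A patient who progresses by PSA at week 10 and is scanned at week 14 contributes an event that precedes the marker. If progression raises uptake, that patient tends to fall in the high-change half because of the progression, and the event is then counted against that half.

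The required week 4-12 PSA in sub-cohort A1 means such events can be recorded. The hypothesis in 2.1, that PET decline goes with PSA response, makes a link between early progression and PET change plausible.

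The stake is interpretation. A positive from-baseline result could be reported as PET change forecasting PSA progression when it may only reflect progression already present at the scan. This is the first secondary objective, and no multiplicity adjustment is planned for secondary endpoints, so a nominal p-value may be taken at face value.

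**Working it through.** **The plan's own figure.** The only power figure is the 89% in 7.2.1, for the primary comparison (40 vs 60, effect size 0.67, two-sided 0.05). With Mann-Whitney efficiency 3/π = 0.955: Φ(0.67 × √(0.955 × 40 × 60/100) − 1.96) = Φ(3.21 − 1.96) = 89.4%; a noncentral t gives 88.8%. It reproduces, but does not concern PSA-PFS. No figure is given for PSA-PFS.

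**Inputs.** From the documents: N = 100 evaluable, SD 30 points (7.2.1), scan at weeks 8-16 or 16-24 (5.3.6), baseline 0-12 weeks before therapy. Assumed, because the documents are silent: exponential PSA-PFS from therapy start with median 20, 26, 35 or 52 weeks; half of scans in each window; censoring at weeks 52-156; PET change unrelated to progression after the scan; an upward PET shift of 0, 10, 20 or 30 points in patients who progressed before it.

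**Share progressing before the scan.** With λ = ln 2/median and scans spread evenly over weeks 8-24, the share is 1 − (e^(−8λ) − e^(−24λ))/(16λ).
- Median 20 weeks: λ = 0.03466; 1 − (0.7579 − 0.4353)/0.5545 = 42%.
- Median 52 weeks: λ = 0.01333; 1 − (0.8989 − 0.7262)/0.2133 = 19%.

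**From-baseline log-rank rejection at nominal 5%** (simulation, 4,000 runs per cell, progression observed continuously):

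| Shift in early progressors | Median 20 wk | 26 wk | 35 wk | 52 wk |
|---|---|---|---|---|
| 20 points | 38.8% | 32.2% | 24.6% | 18.0% |
| 30 points | 68.7% | 58.7% | 44.1% | 30.5% |

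With no shift it is 5-6%, and with 10 points 8-14%. PSA visits every 8 or 12 weeks change little. Across observation patterns and independent re-runs the ranges are about 16-40% at 20 points and 29-69% at 30. These are error rates only for the question whether PET change is associated with progression after the scan.

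**What lowers them.**
- Half of early progressors never scanned: 10-22% at 20 points, 14-41% at 30.
- An extreme stand-in rule that cancels all progressions before week 12 and redraws them later: 6-7% at 20 points, 6-10% at 30.

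**Week-24 landmark** (patients progression-free at week 24, clock from there, split redone).
- Rejection is about 5-6% at shifts of 20 and 30 points, including with PSA every 8-12 weeks.
- If progression is dated at the next, confirming PSA, it is 6-15% at 20 points and 8-29% at 30.
- Patients lost under continuous observation: 1 − 2^(−24/52) = 27% to 1 − 2^(−24/20) = 56%. With PSA every 8-12 weeks, 23-50 of 100.
- Events: 39-51 remain, against 71-96 from baseline.
- Simulated power at an assumed hazard ratio of 1.8 between PET halves, no shift: about 62-73% from baseline, 26-42% at week 24. The usual formula Φ(ln 1.8 × √(d/4) − 1.96) is more optimistic: 70-82% for d = 71-96 and 45-56% for d = 39-51. The simulated values are lower because the sample median does not fall exactly on the true dividing line, and because redoing the split after high-hazard patients have left mixes the two halves.

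**Scan-date landmark.** With PSA every 8-12 weeks, 6-12% at 20 points and 7-19% at 30, because about 5-13 of 100 patients have progression present but not yet recorded. Week 24 is therefore preferable.

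**The case against.** The strongest case is that nothing planned is wrong. Section 2.3 asks only whether PET change is associated with PSA-PFS and states the clock; 3.1 speaks of detecting response; only the rationale in 1.5 looks forward. For concurrent association the log-rank is valid. That stands. A reader might infer that the test has an inflated type I error or should be dropped; the documents do not support this, since the rates above are errors only for the forward-looking question.

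The size is also open to challenge. The 20-point shift equals the PSA50 responder difference in 7.2.1, not a figure for progressors. Section 1.3 reports early rises in PSMA uptake despite PSA response, and 1.4 links low PSMA uptake to aggressive disease; both count against a uniform upward shift. PSA progression is defined by PCWG3, whose text is not in the documents, and a rule that cancels early rises could remove nearly all of the effect. These points stand, so the rates show direction and possible size and are not predictions.

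A landmark costs much of the power and, if progression is dated at confirmation, only partly works. This stands too, and is why it is proposed as supportive and not as a replacement. What the objection does not answer is that no section says how progressions before the scan are treated, or limits what a positive result may be taken to show.

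**Conclusion.** The gap is real and should be fixed, as a matter of what the PSA-PFS comparison can support. As planned, it can show that PET change and PSA progression go together. It cannot by itself show association with subsequent progression, because progression already present at the scan may have set the group.

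How often that would mislead depends on three things the documents do not give: the PSA-PFS median, the PET shift in early progressors and the progression rule. Under the stated assumptions the chance of a significant from-baseline result when PET says nothing about later progression runs from the nominal 5-6% (no shift) to 16-40% (20 points) and 29-69% (30 points), with every early progressor scanned. It could be close to 5% if early rises are cancelled.

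A reader might extend this to overall survival. Patients with a PET group have by definition survived to the scan, but no effect on the OS comparison was quantified and no claim is made about its size. The primary PSA50 analysis is unaffected.

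**What to change.** In 2.3 and 7.4.3:

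1. Keep the from-baseline PSA-PFS comparison and label it concurrent association.
2. Add a supportive landmark analysis, preferably at week 24 after therapy start (the end of the PET window). Restrict it to patients with paired PET and no recorded PSA progression by then, start the clock there, and redo the median split among those patients.
3. Report how many patients progressed before the scan and before the landmark.
4. State whether progression is dated at the first qualifying PSA or at the confirming one.
5. Base any statement about subsequent PSA progression on the landmark analysis.

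The change is wording and one extra analysis. A PSA drawn on the scan day should not be required: the calendars ask only for a value within the week-16 (+/- 8) window, so it would be a new requirement, and the week-24 landmark does not need it.

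The costs are fewer events (about 39-51 against 71-96) and lower power (about 26-42% against 62-73% at a hazard ratio of 1.8). The text should say that a null landmark result is not evidence of no association. PSA after the week-16 value is left to standard of care, so dating of later progression will be uneven. If progression is dated at confirmation, the landmark reduces the problem without removing it.
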